## 8.3 Definitions of analysis sets

All efficacy analyses will be performed using an ITT approach based on the full analysis set. For consistency, demographic and baseline characteristics will be presented using the full analysis set. Safety objectives will be analyzed based on the Safety population.

**All subjects analysis set (All subjects):** This analysis set comprises all subjects screened for the study and will be used for the reporting of disposition and screening failures.

**Biomarker populations:** The biomarker positive and negative populations will be defined in the SAP before un-blinding of this study.

For the reporting of efficacy data, the biomarker positive and negative population will be a subset of the Full analysis set; the primary population for analysis is the biomarker positive population. For the reporting of safety data, the biomarker positive and negative population will be a subset of the Safety analysis set, and for the reporting of PK data, the biomarker positive and negative population will be a subset of the PK analysis set.

### **8.3.1 Efficacy analysis set**

**Full analysis set:** All subjects randomized and receiving any IP will be included in the full analysis set, irrespective of their protocol adherence and continued participation in the study. Subjects will be analyzed according to their randomized treatment, irrespective of whether or not they have prematurely discontinued. For subjects who withdraw consent or assent to participate in the study all data will be included up to the date of their study termination.

### **8.3.2 Safety analysis set**

**Safety analysis set (Safety):** All subjects who received any IP will be included in the safety analysis set. Subjects will be classified according to the treatment they actually received. A subject who has on one, or several occasions, received active treatment will be classified as active. All safety summaries will be based on this analysis set.

### **8.3.3 PK analysis set**

**Pharmacokinetic analysis set (PK):** All subjects in the full analysis set who received Tralokinumab; including PK blood samples that are assumed not to be affected by factors such as protocol deviations (e.g., disallowed medication, or incorrect study medication received). All PK summaries will be based on this analysis set.

### **8.3.4 PRO analysis set**

PRO outcome variables will be evaluated based on the full analysis set.

## **8.4 Outcome measures for analyses**

### **8.4.1 General Definitions**

#### **8.4.1.1 Definition of baseline and subject baseline variables**

For spirometry variables the measurement recorded at the baseline visit (Visit 3) will be used as baseline. If the Visit 3 measurement is missing, the last non-missing value before Visit 3 will be used as baseline instead. For post-BD FEV1, the measurement after the first BD administration is the baseline.

The baseline for the ePRO variables (ACQ-6, AQLQ(s)+12, WPAI-CIQ, and EQ-5D-5L) will be captured on the ePRO device at Visit 3. Baseline for Asthma Daily Diary variables will be the bi-weekly mean for data collected between study day -14 and -1 (i.e. 14 to 1 day before Visit 3).

For laboratory data and physical examination, baseline will be defined as the latest non-missing assessment prior to first dose.

Absolute change from baseline outcome variables is computed as (post-randomization value – baseline value).

Percent change from baseline is computed as  $((\text{post-randomization value} - \text{baseline value}) / \text{baseline value}) \times 100\%$ . If either the post-randomization value or the baseline value is missing, then the absolute or percent change from baseline value will also be set to missing.

#### **8.4.1.2 Visit and period windows**

For the exacerbation-related analyses no windows will be applied.

For the patient reported questionnaires collected in the ePRO, the variables will be summarized based on the protocol scheduled Days with  $\pm$  3-day window.

For the other questionnaires, the window is the same as the protocol-defined visit windows. For local laboratory data, and all vital signs, the visit recorded in the WBDC system will be used.

For the central laboratory results and other endpoints that present visit-based data, the variables will be summarized based on the scheduled days with adjusted analysis-defined visit windows.

A more detailed definition of visit and period windows will be provided in the statistical analysis plan.

### **8.4.2 Calculation or derivation of efficacy variables**

#### **8.4.2.1 Exacerbation rate**

The primary endpoint is the annualised asthma exacerbation rate (AAER) up to Week 52.

In the statistical analysis, the number of asthma exacerbations experienced by a subject during the 52-week double-blind treatment period will be used as response variable, and the logarithm of the subject's corresponding follow-up time will be used as an offset in the analysis to adjust for subjects having different exposure times during which the events occur. Asthma exacerbation is defined in Section 5.1.1

In order to calculate the number of exacerbations experienced by a subject during the 52-week treatment period the following rule will be applied:

- The start of an exacerbation is defined as the start date of systemic corticosteroids, ER or urgent care visits requiring systemic corticosteroids, or hospital admissions due to asthma, whichever occurs earlier, and the end date is defined as the last day of systemic corticosteroids or ER or urgent care visit or hospital discharge, whichever occurs later.

Additional systemic corticosteroid treatments, ER or urgent care visits requiring use of systemic corticosteroids, or inpatient hospitalization due to asthma occurring during an exacerbation should not be regarded as a new exacerbation. In order to be counted as a new exacerbation it must be preceded by at least 7 days in which neither criterion is fulfilled.

Maximum follow-up time for a subject is approximately 52 weeks; defined as the time from randomization to the date of Visit 29. For a subject lost to follow-up, this will be defined as the time from randomization to the time point after which an exacerbation could not be assessed.

For the production of summary statistics, the annual asthma exacerbation rate per subject is calculated, and standardized per a 52-week period according to the formula described below.

*Annual Exacerbation Rate = No. of Exacerbations \* 365.25 / (Follow-up date – Visit 3 date + 1).*

#### **8.4.2.2 Proportion of subjects with $\geq 1$ asthma exacerbation during 52 weeks of treatment**

The proportion of subjects with  $\geq 1$  asthma exacerbation during the 52 weeks of treatment will be a supportive variable to the primary objective. The variable will categorize each subject as having at least one asthma exacerbation or not (yes/no).

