## 8.2 Sample size estimate

The total study sample of 770 subject (385 subjects per group) are considered sufficient to show a reduction in annualised asthma exacerbation rate for tralokinumab, versus placebo in the overall study population.

Sample size calculations in terms of number of subject years needed is based on an assumed annual exacerbation rate in the placebo group of 0.8, and shape parameter of 0.95 (over-dispersion) in both the all-subject and biomarker positive population. The calculations are made for a 1% significance level for all subjects and a 4% significance level for the biomarker positive population. The methodology used described in [Keene et al 2007](#).

Assuming a uniform loss to follow-up of 15% during the study, 770 randomized subjects are expected to provide approximately 355 subject years at risk per treatment group. This is expected to provide at least 90% power for showing superiority with effects down to 37% asthma exacerbation rate reduction in the all-subject population.

The proportion of subjects in the all-subject population falling within the biomarker positive subpopulation will depend on the biomarker positive criteria to be defined in the SAP before un-blinding of this study. Based on results from study D2210C00007, the testing strategy for this study has been revised to use a 5% significance level based on the biomarker positive population as the primary population, and it is estimated that approximately 20% to 35% of the studied subjects will fulfil the biomarker positive criteria. Using a 5% significance level for the biomarker positive population as the primary population, a true asthma exacerbation rate reduction of 50% would have a power between 70% and 90% to show superiority.

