#### **8.4.2.3 Time to first exacerbation**

Time from randomization to the first asthma exacerbation will also be used as a supportive variable to the primary objective, and is calculated as follows:

*Start Date of first asthma exacerbation – Date of Randomization + 1.*

The time to first asthma exacerbation for subjects who do not experience an asthma exacerbation during the treatment period will be censored at the date of their last visit for the 52-week double-blind treatment period, or at the time point after which an exacerbation could not be assessed.

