#### 8.5.7.5 Other endpoints associated with asthma exacerbations

##### Proportion of subjects with $\geq 1$ asthma exacerbation

The proportion of subjects with  $\geq 1$  asthma exacerbation during the 52 weeks of treatment will be addressed as a supportive variable to the primary objective. The proportion of subjects in the active tralokinumab arm will be compared with the proportion in the placebo group in both populations using a Cochran–Mantel–Haenszel test controlled for stratifying variables.

The results of the analyses will be presented as weighted difference in the proportion of subjects who have  $\geq 1$  asthma exacerbation, together with associated 95% CI and 2-sided p-value for each active dose regimen versus placebo. The number and percentage of subjects with  $\geq 1$  asthma exacerbation will also be summarized by randomized treatment for both populations.

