##### Time to first asthma exacerbation

Time to first asthma exacerbation will be analyzed as another supportive efficacy variable to the primary objective to explore the extent to which treatment with tralokinumab delays the time to first exacerbation compared with placebo. A Cox proportional hazard model will be fitted to data with including treatment and at least stratifying variables as covariates.

Results of the analysis will be summarized as hazard ratios, 95% confidence intervals and p-values.

Time to first asthma exacerbation will be displayed graphically using a Kaplan-Meier plot. The median time to event will be summarized by randomized treatment, if there is sufficient uncensored data available to calculate these median values. The percentage of subjects who are exacerbation free at 22 and 44 Weeks will be estimated for each treatment group.

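### The supportive proportion with at least one exacerbation counts subjects lost while event-free as 'no', and no tabulated Week 52 figure accounts for censoring

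*Protocol*

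**What the plan says.** Section 8.4.2.2 defines the variable over the 52 weeks of treatment: "The variable will categorize each subject as having at least one asthma exacerbation or not (yes/no"). It gives no category or rule for incomplete follow-up. Section 8.3.1 keeps every randomized and dosed subject in the full analysis set and uses the data of those who withdraw consent up to study termination.

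Section 8.5.7.5 compares the arms "using a Cochran–Mantel–Haenszel test controlled for stratifying variables". It continues: "The results of the analyses will be presented as weighted difference in the proportion of subjects who have" at least one exacerbation, with a 95% confidence interval and a two-sided p-value.

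For time to first exacerbation, section 8.4.2.3 censors event-free subjects at their last visit of the 52-week period "or at the time point after which an exacerbation could not be assessed". Section 8.5.7.5 then says "Time to first asthma exacerbation will be displayed graphically using a Kaplan-Meier plot", and fixes the numeric read-outs: "The percentage of subjects who are exacerbation free at 22 and 44 Weeks will be estimated for each treatment group".

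The planning assumptions are in section 8.2. The dropout assumption reads "Assuming a uniform loss to follow-up of 15% during the study". The exposure that the sponsor derives from it is given as follows: "770 randomized subjects are expected to provide approximately 355 subject years at risk per treatment group".

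**The concern.** The same first events in the same subjects are handled in two ways. Time to first event censors a subject who leaves early, and the primary rate analysis uses a log follow-up-time offset (sections 8.4.2.1 and 8.5.6). The proportion does neither. A subject who leaves at Week 10 without an event counts the same as one observed event-free to Week 52.

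Two things follow. Each arm's 52-week risk is understated. The between-arm difference also comes to depend partly on how loss is split between the arms, and it is reported with a confidence interval and a p-value.

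Two other provisions might have filled the gap but do not. The missing-data sensitivity analyses in section 8.5.2 name only the primary and key secondary endpoints, and section 2.2 lists this variable under other secondary objectives. The Kaplan-Meier read-outs stop eight weeks before the end of the period over which the endpoint is defined, and the protocol gives no reason for choosing Weeks 22 and 44.

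**Working it through.** **Inputs (section 8.2).** Placebo rate 0.8 per year; dispersion k = 0.95; 15% uniform loss; 385 subjects per arm; rate ratio 0.63 (37% reduction, all subjects) or 0.50 (50% reduction, biomarker positive).

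**Step 1: reproduce the plan's figures.** With loss times uniform over the year, subject-years = 770 × (0.85 + 0.15 × 0.5) = 712, or 356 per arm. The protocol states about 710 and 355.

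Negative binomial Wald power is Φ(|ln RR| / √{[(1/λ0 + k) + (1/λ1 + k)]/T} − z), where T is subject-years per arm.

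- RR 0.63, alpha 1%, T = 355: 0.462/0.1203 − 2.576 = 1.27, so 89.7% (stated: at least 90%).
- RR 0.50, alpha 5%, 20% share, T = 71: 69.0%.
- RR 0.50, alpha 5%, 35% share, T = 124.25: 90.2% (stated range: 70% to 90%).

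Using 1/0.95 as the dispersion gives 88.3%, 67.5% and 89.1%. Reading 0.95 as k therefore fits better.

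**Step 2: 52-week proportion with full follow-up.** With t in years, P(t) = 1 − (1 + kλt)^(−1/k). On placebo, P(1) = 1 − 1.76^(−1.0526) = 44.8%.

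**Step 3: crude yes/no proportion.** Under non-informative uniform loss of fraction d, crude = (1 − d) × P(1) + d × M. Here M is the average of P(t) over the year: M = 1 − [(1 + kλ)^(1−1/k) − 1] / [kλ(1 − 1/k)].

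- Placebo: M = 26.712%; 0.85 × 44.847 + 0.15 × 26.712 = 42.127%.
- RR 0.63: M = 19.124%; 0.85 × 33.756 + 0.15 × 19.124 = 31.561%.
- RR 0.50: M = 15.955%; 0.85 × 28.754 + 0.15 × 15.955 = 26.834%.

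Differences below come from unrounded values.

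| | Full follow-up | Crude, 15% loss | Shortfall (points) |
|---|---|---|---|
| Placebo | 44.8% | 42.1% | 2.7 |
| RR 0.63 | 33.8% | 31.6% | 2.2 |
| RR 0.50 | 28.8% | 26.8% | 1.9 |
| Difference, RR 0.63 | 11.1 points | 10.6 points | 0.5 |
| Difference, RR 0.50 | 16.1 points | 15.3 points | 0.8 |

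**Step 4: unequal loss.** The splits here are assumptions and are not in the protocol.

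| Loss, placebo / active | Crude difference, RR 0.63 (full: 11.1) | Crude difference, RR 0.50 (full: 16.1) |
|---|---|---|
| 20% / 10% | 8.9 | 13.7 |
| 10% / 20% | 12.2 | 16.8 |

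With no treatment effect and both arms at rate 0.8, each percentage point of extra loss costs (44.847 − 26.712)/100 = 0.181 points. A 10% against 20% split then gives a difference of 1.8 points.

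**Step 5: what the Week 44 read-out leaves out.** P(44/52) is 40.7% on placebo, 30.1% at RR 0.63 and 25.4% at RR 0.50. Between 3.3 and 4.1 points of first events fall after the last listed landmark.

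**The case against.** - **The coding is narrower than it may look.** A reader might infer that all dropouts are treated as event-free. They are not. A subject with an event before leaving is coded *yes*, and only those lost while event-free default to *no*. That default follows from the definition and the analysis set, not from a stated rule. Subjects who only stop treatment are a different group: section 4.2 offers three follow-up options that collect exacerbation information to Week 52, and section 5.1.1 counts events after treatment stops. This stands.
- **A censoring-aware 52-week estimate is already implied.** A reader might infer that nothing planned gives a valid 52-week proportion. The documents do not support that. The Kaplan-Meier curve is not said to stop at Week 44, and the censoring rule carries it to about Week 52. What is missing is the tabulated number. This stands.
- **The SAP may settle it.** It is not at hand, and follow-up rules for a supportive binary variable often sit there. That is fair as to detail. However, the protocol itself fixes the estimator, the test and the two landmark weeks.
- **The effect is small.** From the Step 2 proportions, the binomial standard error of the difference is about 3.4 to 3.5 points with 385 per arm, and about 5.8 to 7.8 points with 77 to 135 per arm in the biomarker positive population (20% to 35% of 385). Even the assumed 1.8-point null shift is below one null standard error, √(2 × 0.448 × 0.552/385) = 3.6 points. This stands and limits the severity.
- **Kaplan-Meier is not unbiased in general.** It needs non-informative censoring. True, but the crude proportion is too low even when that condition holds.

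**Conclusion.** The point holds in a limited form. The crude proportion understates each arm's 52-week risk by 1.9 to 2.7 points under the protocol's own 15% equal loss. It moves the difference toward no effect by 0.5 to 0.8 points. No listed numeric estimate of the 52-week proportion accounts for censoring.

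These sizes assume the negative binomial planning model, k = 0.95, and uniform, non-informative loss. A bias in favour of the drug appears only under unequal loss, for which the protocol gives no figures. No confirmatory claim is at risk: sections 8.4.2.2 and 8.5.7.5 call the variable supportive, it has no step in the hierarchy of section 8.5.1, and both the primary model and the Cox model allow for unequal follow-up. This is a minor improvement to the stated estimator.

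**What to change.** In section 8.5.7.5, add Week 52 to the Kaplan-Meier read-outs and state the study day at which it is read, since completers are censored around Visit 29. Report 1 minus the Kaplan-Meier estimate at that day per arm, and the between-arm difference with a Greenwood-based 95% confidence interval, as the estimate of the 52-week proportion. State that it assumes non-informative censoring.

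Keep the crude counts and the Cochran–Mantel–Haenszel comparison as description. In section 8.4.2.2, say explicitly how a subject lost while event-free is coded. Weeks 22 and 44 can stay if there is a reason for them.

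The cost is wording and one table row. The data and the curve are already planned.

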#### **8.4.2.3 Time to first exacerbation**

Time from randomization to the first asthma exacerbation will also be used as a supportive variable to the primary objective, and is calculated as follows:

*Start Date of first asthma exacerbation – Date of Randomization + 1.*

The time to first asthma exacerbation for subjects who do not experience an asthma exacerbation during the treatment period will be censored at the date of their last visit for the 52-week double-blind treatment period, or at the time point after which an exacerbation could not be assessed.

#### **8.4.2.4 Forced expiratory volume in 1 second**

The key secondary variable is the pre-dose/pre BD FEV1

The percent change from baseline to each of the post-randomization visits (post Visit 3), up to and including the end of 52-week double-blind treatment visit (Visit 29), will be used as secondary efficacy outcome variable.

The absolute change from baseline to each of the post-randomization visits (post Visit 3) up to and including the end of 52-week double-blind treatment visit (Visit 29) will be used as a outcome variable.

The same outcome variables will be derived for the secondary variable pre-dose/post- BD FEV1.

#### **8.4.2.5 Annualised asthma exacerbation rate associated with an ER or urgent care visit or a hospitalization**

The annual rate of asthma exacerbations that are associated with an ER or urgent care visit or a hospitalization will be a secondary efficacy variable.

The number of asthma exacerbations that are associated with an ER or urgent care visit or a hospitalization experienced by a subject during the 52-week treatment period will be derived using the same rule for start and end as described for the primary variable in section 8.4.2.1.

In the statistical analysis, the number of asthma exacerbations that are associated with an ER or urgent care visit or a hospitalization experienced by a subject during the 52-week double-blind treatment period will be used as response variable, and the logarithm of the subject's corresponding follow-up time will be used as an offset in the analysis to adjust for subjects having different exposure times during which the events occur.

Maximum follow-up time is approximately 52 weeks, and the follow-up time is derived as described in Section 8.4.2.1

Additionally, for the production of descriptive statistics, the annualised rate of asthma-related ER or urgent care visits and hospitalizations will be calculated using the same methodology as the annualised rate of exacerbations described in Section 8.4.2.1.

#### **8.4.2.6 Forced Vital Capacity and Forced Expiratory Flow at 25-75%**

The percent change from baseline to each of the post-randomization visits, up to and including the end of 52-week double-blind treatment visit (Visit 29/EOT) will be calculated for the exploratory variables FVC and FEF25-75%.

### **8.4.3 Calculation or derivation of patient reported outcome variables**

Patient-reported outcomes data will be captured via an ePRO device. The definition of key secondary and secondary outcome variables are provided in the following sections.

#### **8.4.3.1 Asthma symptom score**

Asthma symptoms during night-time and daytime will be recorded by the subject each morning and evening in the Asthma Daily Diary. Symptoms will be recorded using a scale 0-3, where 0 indicates no asthma symptoms. Asthma symptom daytime score, night-time score, and total score will be calculated separately.

The total daily symptom score will be calculated by taking the sum of the daytime and night-time asthma symptom scores for each day. If a subject is missing a value for either daytime or night-time asthma symptom score on a given day then the total score for that day will be set to missing.

The key secondary outcome variable is the biweekly mean daily asthma symptom total score. The daily asthma symptom total score is defined as the sum of the daytime and night-time symptom scores as captured in the Asthma Daily Diary. The biweekly mean is calculated as the mean daily asthma symptom total over 14 sequential days. If more than 7 daily scores (>50%) within that period is missing, then the daily asthma symptom mean score is set to 'missing'.

#### **8.4.3.2 Rescue medication use**

The number of rescue medication inhalations and nebulizer treatments taken will be recorded by the subject in the Asthma Daily Diary twice daily.

The number of inhalations of rescue medication captured in the eDiary each day will be calculated per subject. If a subject is missing a value for either morning or evening rescue medication on a given day, then the total rescue medication use for that day will be set to missing.

Total rescue medication use, defined as the average number of inhalations (puffs) per day will be calculated as the outcome variable.

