### **5.1 Efficacy assessments**

#### **5.1.1 Assessment of asthma exacerbations**

For the purpose of the protocol, an asthma exacerbation will be defined as a worsening of asthma that leads to any of the following:

- Use of systemic corticosteroids for at least 3 days; a single depo-injectable dose of corticosteroids will be considered equivalent to a 3-day course of systemic corticosteroids

- An ER or urgent care visit (defined as evaluation and treatment for <24 hours in an ED or urgent care center) due to asthma that required systemic corticosteroids (as per above)
- An inpatient hospitalization (defined as admission to an inpatient facility and/or evaluation and treatment in a healthcare facility for  $\geq 24$  hours) due to asthma

The ePRO device will be programmed to alert both the subject and study site when certain pre-specified worsening thresholds are crossed as follows:

- Decrease in morning peak flow  $\geq 30\%$  on at least 2 of 3 successive days compared with baseline (last 10 days of run-in), and/or
- A  $\geq 50\%$  increase in rescue medication or one new or additional nebulized  $\beta_2$ -agonist on at least 2 of 3 successive days compared with the average use for the previous week, and/or
- Nocturnal awakening due to asthma requiring rescue medication use for at least 2 of 3 successive nights, and/or;
- An increase in total asthma symptom score (the sum of day time [evening assessment] and night-time [morning assessment] of at least 2 units above the run-in average (last 10 days of run-in), or the highest possible score (daily score of 6), on at least 2 of 3 successive days.

For the purpose of the protocol, worsening of asthma is defined as new or increased symptoms and/or signs (i.e., physical examination or lung function) that can be either concerning to the subject (subject-driven) or related to an Asthma Daily Diary alert (diary-driven).

If an exacerbation event is not associated with deterioration in at least one of the pre-specified subject-driven and/or diary-driven objective measurements, the Investigator will have to justify the decision for defining the event as an exacerbation. Events that are not supported by any objective assessment will be deemed not to be a protocol-defined exacerbation.

In order to calculate the number of exacerbations experienced by a subject during the 52-week treatment period, the following rule will be applied:

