### **Rescue medication**

The number of rescue medication inhalations (puffs) and nebulizer treatments taken will be recorded by the subject in the Asthma Daily Diary twice daily (i.e., in the morning and in the

evening) beginning the evening of Visit 2 until the morning of Visit 29. The number of inhalations taken between the morning and evening lung function assessments will be recorded in the evening. The number of inhalations taken between the evening and the morning will be recorded in the morning.

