#### **7.7.2 Restrictions during and after the study**

##### **7.7.2.1 Asthma medication restrictions**

##### **Use of short-acting $\beta_2$ -agonists (SABA)**

Regularly scheduled SABA use in the absence of any asthma symptoms is discouraged from enrollment and throughout the study duration.

Prophylactic use of SABA (e.g., prior to planned exercise) if deemed necessary by the subject and the Investigator, may be used, but should **not** be recorded in the Asthma Daily Diary. Any such use should be documented in medical notes and recorded in the eCRF.

SABA via a metered dose device is permitted as needed for worsening asthma symptoms (i.e., rescue use) and will be recorded in the Asthma Daily Diary as number of inhalations.

Rescue use of SABA administered via jet or ultrasonic nebulization is allowed. Occasions where SABA was administered via nebulization will be recorded separately from metered dose inhaler inhalations in the Asthma Daily Diary.

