##### **Rescue medication use**

Total rescue medication use (average puffs/day) will be analyzed as the response variable by fitting a linear model to the data. Treatment group will be fitted as the explanatory variable, and at least stratifying variables will be fitted as covariates. The results will be presented in terms of LSMEANS, difference between treatments in LSMEANS and 95%CI. The number and percentage of subjects within each treatment group who received rescue medication will be summarized by visit.

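### The outcome for total rescue medication use is defined in inhaler puffs only, so nebulised rescue, which is permitted and separately recorded, does not enter it

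*Protocol*

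**What the plan says.** **Collection.** Section 8.4.3.2 begins: "The number of rescue medication inhalations and nebulizer treatments taken will be recorded by the subject in the Asthma Daily Diary twice daily". The diary description in Section 5.2.2.1 likewise names two quantities: "The number of rescue medication inhalations (puffs) and nebulizer treatments taken will be recorded by the subject". Section 7.7.2.1 permits the nebulised route ("Rescue use of SABA administered via jet or ultrasonic nebulization is allowed") and keeps its record apart: "Occasions where SABA was administered via nebulization will be recorded separately from metered dose inhaler inhalations in the Asthma Daily Diary".

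**Derivation.** Having named both items, Section 8.4.3.2 carries one forward: "The number of inhalations of rescue medication captured in the eDiary each day will be calculated per subject". It then defines the outcome: "Total rescue medication use, defined as the average number of inhalations (puffs) per day will be calculated as the outcome variable".

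**Analysis.** Section 8.5.7.8 repeats the unit: "Total rescue medication use (average puffs/day) will be analyzed as the response variable by fitting a linear model to the data". The model has treatment and, as a minimum, the stratifying variables. The only other rescue summary there is a by-visit count and percentage of subjects who received any rescue medication.

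**Alert.** Section 5.1.1 lists the diary thresholds for worsening. One is met either by a rise of at least 50% in rescue medication or by "one new or additional nebulized" beta2-agonist, on at least 2 of 3 successive days.

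**Status.** Section 2.2 lists rescue medication use among the other secondary outcomes. It does not appear in the nine testing steps of Section 8.5.1.

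**The concern.** The objective is rescue medication use as a measure of asthma control. The variable that serves it leaves out one of the two permitted and recorded forms of rescue. That form is the one the protocol itself treats as a sign of deterioration, so the omission falls on days when rescue use should be counted most carefully.

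Two sections state the same rule, so this is a fixed definition and not a detail left for the SAP. An analyst who follows it will drop nebuliser data already in the database, and the reported mean will understate rescue use wherever nebulisers are used. If nebuliser use differs between arms, the treatment contrast is distorted. If it is more common on placebo, the distortion works against tralokinumab.

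**Working it through.** The protocol gives no figure that depends on rescue use, so there is none to reproduce. The check sets the definition beside the collected data and then looks at the direction of the score.

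**1. Can inhalations be read to include nebulisations?** No. Section 5.2.2.1 equates inhalations with puffs and names nebuliser treatments beside them. Section 7.7.2.1 ties the count of inhalations to the metered dose device and separates nebulised use from it. Section 8.5.7.8 gives the unit as puffs per day.

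**2. Is nebuliser use picked up elsewhere?** Only in part. The by-visit count of subjects with any rescue medication may include nebuliser users, but it is descriptive and does not measure amount. ACQ-6 has one rescue item among six. There is no conversion and no nebuliser outcome.

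**3. Direction of the score.** Let P be puffs per day, N nebuliser treatments per day and k the puffs counted for one nebuliser treatment.

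- Protocol score: S = P
- Use with both forms counted: U = P + k × N
- Changes: ΔS = ΔP and ΔU = ΔP + k × ΔN
- When ΔP is negative and ΔN is positive, S falls while U rises if k > −ΔP/ΔN.

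The protocol gives no k, so it is varied from 1 to 10 as an assumption. The usage patterns are also assumed. Each starts from P = 4, N = 0, so S = U = 4.

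| Pattern afterwards | S | U at k = 1 | k = 2 | k = 4 | k = 8 | k = 10 | Use has risen if |
|---|---|---|---|---|---|---|---|
| Partial replacement: 1 puff + 2 nebulisations | 1 | 3 | 5 | 9 | 17 | 21 | k > 3/2 = 1.5 |
| Full replacement: 0 puffs + 2 nebulisations | 0 | 2 | 4 | 8 | 16 | 20 | k > 4/2 = 2 |
| Addition: 4 puffs + 2 nebulisations | 4 | 6 | 8 | 12 | 20 | 24 | k > 0 |

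With replacement the score drops by 3 or 4 puffs/day. With addition it stays at 4, and the extra use is missed.

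**4. Effect on the contrast between arms.** The protocol gives no frequency of nebuliser use. For illustration only, assume that 5% of placebo and 2% of active subjects each replace 4 puffs/day:

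- Replacement throughout the averaging period: 0.05 × 4 − 0.02 × 4 = 0.20 − 0.08 = 0.12 puffs/day.
- Replacement for 10 days of a 364-day averaging period: 0.12 × 10/364 = 0.003 puffs/day.

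The assumed duration alone moves the result about 36-fold, so neither figure is an estimate for this trial.

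**The case against.** **The word total may mean something narrower.** In Section 8.4.3.2 a day's total is set to missing if the morning or evening entry is missing, and Section 8.4.3.1 builds the symptom total from daytime and night-time scores. On that reading the variable is a deliberate measure of inhaler puffs over both diary entries, with consistent units. This is a fair account of how the label may have arisen. It does not explain why the section opens with two recorded items and gives no use for the second, or how the measure serves an objective stated as rescue medication use without restriction.

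**A reader might infer that anyone who worsens and moves to a nebuliser will appear to improve.** The documents do not support that in general. The score falls only when nebulisations replace puffs, and the alert wording also covers nebulisations taken on top of them, where worsening is missed but not reversed. The analysed variable is an average level. The protocol defines no change or responder score for rescue use, so no subject is classed as improved.

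**A reader might infer that the model wrongly omits baseline rescue use.** Section 8.5.7.8 sets the stratifying variables as a minimum, so baseline may be added and the SAP, not available here, may do so. Under randomisation, leaving it out mainly costs precision.

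**The consequence is small.** This stands. The outcome is outside the testing hierarchy, nebuliser-related worsening is monitored through the alert, and ACQ-6 carries some rescue information. If nebuliser use is more common on placebo, the error does not produce a false claim of benefit.

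**Conclusion.** The point holds as a minor flaw in a stated definition. Sections 8.4.3.2 and 8.5.7.8 leave out rescue use that the protocol permits, records and elsewhere treats as a sign of worsening. The outcome misses nebulisations that are added to puffs and falls when they replace puffs.

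The direction follows from the definition. Whether a falling score accompanies rising use depends on the puff equivalent: above 1.5 or 2 in the two assumed replacement patterns. It would be going too far to say that a known amount of benefit is masked. Frequency of nebuliser use, its duration, its split between arms and the equivalent are all absent from the protocol. The primary endpoint, key secondary endpoints and type I error control are unaffected.

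**What to change.** Before unblinding, choose one of two routes and align Sections 8.4.3.2 and 8.5.7.8:

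- **Count both forms.** Define total daily use as puffs plus nebuliser treatments times one fixed, pre-stated equivalent, used for analysis only. Derive it identically at baseline and after baseline, and report puffs-only as supportive.
- **Narrow the label.** Rename the variable as inhaler puffs per day and report nebuliser treatments as a separate outcome.

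As a companion change, name baseline rescue use as a covariate in the linear model. Section 8.4.1.1 already defines the diary baseline over study days -14 to -1, and the models in Sections 8.5.7.2 to 8.5.7.4 already adjust for their own baselines. The current wording permits this but does not require it.

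The cost is a derivation line and a covariate, with no new data and no change to treatment. The downside of the first route is that the equivalent is a convention. The supportive puffs-only analysis shows how far the result depends on it.
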